Overall effectiveness will be evaluated by tracking daily opioid usage 90 days postoperatively in both SOC and SOC+VR groups. Average MMEs (Morphine Milligram Equivalents) per day will be compared using unpaired Student's *t*-test (or the nonparametric Wilcoxon rank-sum test) in interim and final endpoint analyses. In addition, changes in usage over time will be evaluated using linear mixed models (or nonlinear models, given data shape), accounting for variations in recovery time across patients and other covariates, such as other analgesic medications used postoperatively, preoperative opioid use, and dosage changes. A sub-analysis will compare usage in the 14-day acute postoperative recovery period.

The secondary endpoint of this study is a comparison of the cumulative experience of pain over the 14-day acute postoperative period between SOC and SOC+VR groups. In order to quantify pain that fluctuates over time, NPRS pain scores will be plotted for each patient over the acute postoperative period, using straight-line interpolation between measurements. This approach will allow for incorporation of all data collected (even if some patients participate more than others), and will avoid overemphasis on a single outcome measure (e.g. pain on day 14). Percent-areaunder-the-curve (VAS-%AUC) measurement will be calculated for each patient by adding the

PI Name: [name] Research Protocol: July 25, 2019 Version 1.2 (03/17/20)

areas of consecutive trapezoids defined by time on the x-axis and pain level measurements on the y-axis (e.g. 100% would indicate pain scores of 10 across the entire time period; 50% would indicate a linear reduction from 10 to 0 over the same time period). In interim and final endpoint analyses, NPRS-%AUC accumulated to date will be compared between groups using an unpaired Student's *t*-test (or nonparametric equivalent). In addition, linear mixed models will be used to compare cumulative pain between SOC and SOC+VR groups over time, as well as pain experienced in the inpatient postsurgical period and following days.

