Additional outcome data will be compared between groups in preliminary analyses using chisquared tests (for categorical variables), unpaired Student's t-tests (for single-measure normal continuous data), or nonparametric equivalent (for non-normal data), as appropriate. For measures collected at multiple time points, %AUC values will be calculated per patient and compared using aforementioned tests. In final analyses, outcomes will be compared using linear mixed models, allowing for data missing at random and evaluation of covariates.

When approximately 25% of the total required sample has been collected, patient data will be summarized to verify adequate study power, and interim analyses will be conducted. In order to preserve a Type I error rate of 5% (i.e., $\alpha = 0.05$) for final analyses, interim analyses will be conducted with *p*-value threshold of 0.001, as suggested using the Hybittle-Peto method, meaning that only effects where d > 2.0 will be significant. Additional patients may be recruited as needed to ensure sufficient study power, and fewer patients may be recruited if interim analyses demonstrate highly significant effects. All statistical analyses will be performed with SAS (SAS 9.4, SAS Institute, Cary, NC), Stata (SE 14.2, StataCorp, LLC, College Station, TX), or R (R 3.5.2, The R Foundation, Vienna, Austria) statistical software, with p-values of <0.05 considered statistically significant.

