5.6.1 Sample Size Considerations

This study has been designed with consideration for power requirements of both primary and secondary endpoint evaluations, as well as requirements for a noninferiority trial evaluating the overall effectiveness of RelieVRx as an opioid-sparing product.

Primary Endpoints

Preliminary data collected at Geisinger Medical Center (Danville, PA) between March 2017 and December 2018 from 1,052 patients who underwent total joint arthroplasty showed an average postoperative pain score of 8.50 following the procedure, and 6.16 on day 2 (SD = 2.0; change d = 1.2, or a 28% pain reduction) under SOC.

To assess the acute effectiveness endpoint of 20% average reduction in pain scores, each onesample *t*-test only requires data from 13 patients to demonstrate a significant difference from zero, assuming 20% attrition, a Type I error rate of 5% and a Type II error rate of 20% (i.e., 80%

PI Name: [name] Research Protocol: July 25, 2019 Version 1.2 (03/17/20) power). In order to observe significance of a lower threshold (e.g., a 10% reduction in pain level on average), data from **43 patients using VR** will be required, assuming 20% attrition, a Type I error of rate 5% and 80% power.

To assess the overall effectiveness for reducing opioid usage by at least 20%, this study assumes an average MME per day of 12.5mg (SD = 3) across all users, although continuous opioid users may report averages higher than 50mg/day. Observing a 20% relative reduction in opioid usage in the SOC+VR group compared to SOC (2.5mg) will require **64 patients total (32 per group)**, assuming 25% attrition, a Type I error rate of 5% and 80% power. If interim data analysis reveals unexpectedly high variability in opioid consumption, a revised power calculation based on new data may increase data collection requirements to address this question.

Secondary Endpoint

Using aforementioned preliminary data, two patients groups were created with simulated VAS-%AUC data (with day 14 VAS means of 6.16 and 4.93, SD = 2.0; or, a 20% greater reduction at day 14) corresponding to a 7% difference in VAS-%AUC (0.86 versus 0.79; SD = 0.1; difference d = 0.7). Assuming 25% attrition, the study will require **92 patients total** (**46 per group**). Data from at least 68 patients is needed to observe a statistically significant VAS-%AUC difference between SOC and SOC+VR of 7% in an unpaired *t*-test, with a Type I error rate of 5% and 80% power.

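### Type I error control at 5% is not guaranteed: patients may be added after a between-arm interim look, under no stated rule, and the final test stays at 0.05

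*Combined protocol and SAP*

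**What the plan says.** Section 5.6 times the look as follows: "When approximately 25% of the total required sample has been collected". What happens then is described in these terms: "patient data will be summarized to verify adequate study power, and interim analyses will be conducted". Mean MME per day is compared between the groups "in interim and final endpoint analyses", and the pain %AUC is likewise compared between groups at both times. The treatment difference is therefore calculated at the look where power is checked.

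The interim tests use a "threshold of 0.001, as suggested using the Hybittle-Peto method". The stated purpose is "In order to preserve a Type I error rate of 5" percent for the final analyses. Section 5.6 then says "Additional patients may be recruited as needed to ensure sufficient study power". The same sentence allows a smaller trial if the interim effects are highly significant. Final significance is judged "with p-values of <0.05 considered statistically significant".

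Section 5.6.1 names one specific trigger for an increase, higher than expected variability in opioid use. In that case "a revised power calculation based on new data may increase data collection requirements to address this question". It does not say that this variability is computed without treatment codes, or that it is the only permitted basis for an increase.

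**The concern.** A stringent interim threshold limits the chance of a false early rejection. It does nothing about a second route to error, in which the final sample size depends on the interim difference and the ordinary pooled test is then applied as if the size had been fixed. The null distribution of that final statistic depends on the rule for adding patients, and the plan gives no rule.

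At stake is the 5% that Section 5.6 says is preserved. Section 8 says the data will go into a de novo submission to the FDA, where a discretionary increase after a look at the effect would be hard to defend afterwards. The documents also do not say who sees the comparative interim result, in a trial whose intervention is plainly visible to patients and staff.

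**Working it through.** **Inputs.** From Section 5.6: one look at information fraction 0.25, interim p < 0.001 (|Z| > 3.291), final p < 0.05 (|Z| > 1.960). From Section 5.6.1: MME difference 2.5 mg/day with SD 3, %AUC difference 0.07 with SD 0.1, 25% attrition. Sidedness is not stated. Two-sided is assumed because it reproduces the plan's sample size.

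**The plan's own figures.**
- Opioid endpoint: d = 2.5/3 = 0.833. A two-sided t-test at 80% power needs 23.6, so 24 per arm, and 24/0.75 = 32 per arm, 64 in total. This agrees.
- %AUC: d = 0.7 needs 34 per arm (68), and 34/0.75 = 45.3, so 46 per arm, 92 in total. This agrees.
- The remark in Section 5.6 that only d > 2.0 would reach 0.001 fits a between-arm t-test on 25% of 64 = 16 patients: 4.14 × √(2/8) = 2.07.

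**Baseline with the size fixed.** Let R be the final size as a multiple of the plan and z the interim statistic. Under the null, the chance that the ordinary final test rejects, given z, is

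CE(z, R) = 1 − Φ[(1.96√R − 0.5z)/√(R − 0.25)] + Φ[(−1.96√R − 0.5z)/√(R − 0.25)].

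Overall error = 0.001 + ∫ CE(z, R(z)) φ(z) dz over |z| < 3.291. With R = 1 throughout this is 0.0506, the usual small Hybittle-Peto excess over 0.05. It is the right comparator for the figures below.

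**Why the rule matters.**
- At z = 0, R = 1: 1.96/√0.75 = 2.263, so CE = 2 × 0.0118 = 0.0236. At R = 2: 2.772/√1.75 = 2.095, so CE = 2 × 0.0181 = 0.0361. Enlarging after a flat interim raises the error.
- At z = 1.2, R = 1: CE = 0.0582 + 0.0016 = 0.0597 (unrounded terms). At R = 2: CE = 0.0503 + 0.0054 = 0.0557. Enlarging after a promising interim lowers it.

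**Overall error under assumed rules.** Resetting to 80% power at the observed effect means R = (1.960 + 0.842)²/(4z²) = 1.96/z², held between 1 and the cap.

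| Rule for adding patients | Cap 1.5× | Cap 2× | Cap 4× |
|---|---|---|---|
| None (size fixed) | 5.06% | 5.06% | 5.06% |
| Reset to 80% power at observed effect | 5.47% | 5.69% | 6.01% |
| Worst case over any effect-driven increase | 5.49% | 5.71% | 6.04% |
| To 80% conditional power, only if already ≥ 30% | 5.09% | 5.11% | 5.12% |
| To 80% conditional power, only if already ≥ 50% | 5.05% | 5.05% | 5.05% |

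With no practical cap the worst case is 6.38%.

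**Variance-driven increases.** These were simulated with t-tests, 1,000,000 trials per setting, 6 to 12 per arm at the interim and true SD 3 to 6. Error was 5.02% to 5.09% with a blinded SD, against 5.02% to 5.10% with the size fixed. Using the within-group SD from unblinded data gave 5.10% to 5.31%.

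**The case against.** A reader might infer that the 5% level is definitely lost, or that it is lost whenever the observed difference influences the size. The documents do not support either statement. No section says the size will be raised on the observed effect. Section 5.6 links the effect only to recruiting fewer patients, and the one named trigger for more is variability. Even an effect-based increase leaves the error at 5.05% if it is made only when conditional power is already at least 50%. The inflation is also modest: against the 5.06% baseline, the reset rule adds about 0.4 points at 1.5× and 0.6 at 2×, and reaches about 1 point only at 4×.

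All of that stands, and it limits the claim to control that is not guaranteed. It does not remove the point. The variability trigger in Section 5.6.1 concerns opioid use only and is neither described as blinded nor made exclusive, while the permission in Section 5.6 is general and sits beside an assurance of 5%.

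A reader might also infer that the staff who coach patients on the headset would know the interim effect. The documents do not say who runs or sees the analysis. The gap is real, but that consequence is not established.

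**Conclusion.** The plan asserts a 5% Type I error that its text does not secure. For the between-arm opioid and %AUC tests, the error could lie anywhere from essentially the fixed-size 5.06% to about 6.0% at a fourfold cap, depending on a rule the plan leaves open. This rests on a two-sided test, one look at 25% information, a single between-arm endpoint, and resizing rules and caps that are assumptions. The figures do not carry over directly to the one-sample endpoint on pain change after VR use, although the same principle applies. The size of the effect makes this a point that should be corrected, not one that undermines the trial.

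**What to change.** In Section 5.6, replace only the clause "Additional patients may be recruited as needed to ensure sufficient study power" with:

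> The sample size may be increased once, up to a stated cap, using only the pooled SDs of MME/day and NPRS-%AUC computed without treatment codes, and observed attrition, with the planned differences (2.5 mg/day; 7% AUC) held fixed. The observed treatment difference will not be used to increase the sample size.

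Keep the clause on recruiting fewer patients and tie it explicitly to p < 0.001. It is the plan's only stated consequence of crossing that threshold. %AUC needs to be included because it drives the largest stated requirement (92 patients, against 64 for opioid use). In Section 5.6.1, state that the variability check is blinded. Add that comparative interim results are available only to the person who runs the analysis.

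If the sponsor wants effect-based increases, pre-specify a fixed-weight inverse-normal test for the final analysis instead: Z = √0.25·Z₁ + √0.75·Z₂, where Z₁ and Z₂ come from the data before and after the look. Under any rule for adding patients, its error is 5.06% with a cut-off of 1.960, or 5.00% with 1.965 (nominal p = 0.0494).

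The cost is wording. The sponsor gives up effect-based enlargement with the ordinary test. The pooled SD runs slightly high if VR works as planned: √(3² + 1.25²) = 3.25 against 3 for MME/day.

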5.6.1 Sample Size Considerations

This study has been designed with consideration for power requirements of both primary and secondary endpoint evaluations, as well as requirements for a noninferiority trial evaluating the overall effectiveness of RelieVRx as an opioid-sparing product.

Primary Endpoints

Preliminary data collected at Geisinger Medical Center (Danville, PA) between March 2017 and December 2018 from 1,052 patients who underwent total joint arthroplasty showed an average postoperative pain score of 8.50 following the procedure, and 6.16 on day 2 (SD = 2.0; change d = 1.2, or a 28% pain reduction) under SOC.

To assess the acute effectiveness endpoint of 20% average reduction in pain scores, each onesample *t*-test only requires data from 13 patients to demonstrate a significant difference from zero, assuming 20% attrition, a Type I error rate of 5% and a Type II error rate of 20% (i.e., 80%

PI Name: [name] Research Protocol: July 25, 2019 Version 1.2 (03/17/20) power). In order to observe significance of a lower threshold (e.g., a 10% reduction in pain level on average), data from **43 patients using VR** will be required, assuming 20% attrition, a Type I error of rate 5% and 80% power.

To assess the overall effectiveness for reducing opioid usage by at least 20%, this study assumes an average MME per day of 12.5mg (SD = 3) across all users, although continuous opioid users may report averages higher than 50mg/day. Observing a 20% relative reduction in opioid usage in the SOC+VR group compared to SOC (2.5mg) will require **64 patients total (32 per group)**, assuming 25% attrition, a Type I error rate of 5% and 80% power. If interim data analysis reveals unexpectedly high variability in opioid consumption, a revised power calculation based on new data may increase data collection requirements to address this question.

Secondary Endpoint

Using aforementioned preliminary data, two patients groups were created with simulated VAS-%AUC data (with day 14 VAS means of 6.16 and 4.93, SD = 2.0; or, a 20% greater reduction at day 14) corresponding to a 7% difference in VAS-%AUC (0.86 versus 0.79; SD = 0.1; difference d = 0.7). Assuming 25% attrition, the study will require **92 patients total** (**46 per group**). Data from at least 68 patients is needed to observe a statistically significant VAS-%AUC difference between SOC and SOC+VR of 7% in an unpaired *t*-test, with a Type I error rate of 5% and 80% power.

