5.6 STUDY ENDPOINTS AND STATISTICAL PLAN

This study will evaluate two primary endpoints – effectiveness of a single use of RelieVRx in the reduction of acute postoperative pain by 20%; and overall effectiveness of RelieVRx as an opioid-sparing intervention, where opioid and non-opioid consumption is reduced by at least 20% over a 90-day postoperative period in the SOC+VR group compared to the SOC group.

Acute effectiveness will be evaluated using NPRS data collected before and after each use of RelieVRx (up to 3 times per day) over the 14-day postoperative period. NPRS is measured on a scale of 0-10, with 0 being the least amount of pain and 10 being the most. Because pain levels will vary by time of day administered and are expected to peak in the first 24-72 hours postoperatively and drop afterward, acute effectiveness will be evaluated at all stages of recovery. The expected 20% reduction after single use will be scaled relative to the pre-use pain score [e.g. users reporting a pre-VR pain level of 8 would need to report post-VR pain levels of 6.4 (8 * 80%) on average; users reporting pre-VR pain of 5 would need to report pain levels of 4 post-VR, etc.]. Each SOC+VR patient will use VR up to 44 times over the 14-day recovery period, requiring linear mixed model analysis to assess acute changes in pain scores while accounting for stage of recovery and other covariates, such as age, preoperative health status and opioid use, and postoperative complications. For interim and final endpoint analyses, pain %change scores will be calculated for each use and averaged for each patient across the 72-hour acute postoperative period, the following week, after 10 days, and overall. These averages will be evaluated using one-sample unpaired *t*-tests (or the nonparametric one-sample Wilcoxon signed-rank test, as needed for non-normal data).

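### The acute primary endpoint is a 20% relative drop in pain, but its tests are against zero, judged by p<0.05 alone, in four windows with none decisive; the opioid primary also lacks a rule for 20%

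*Combined protocol and SAP*

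**What the plan says.** Section 5.6 gives the first primary endpoint as "effectiveness of a single use of RelieVRx in the reduction of acute postoperative pain by 20" percent. The scale is explicit: "The expected 20% reduction after single use will be scaled relative to the pre-use pain score". An example follows: "users reporting a pre-VR pain level of 8 would need to report post-VR pain levels of 6.4 (8 * 80%) on average". Specific Aim 1 (Section 4.1) words the target differently, as at least 20% or 2 points after each use.

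For the interim and final endpoint analyses, "pain %change scores will be calculated for each use and averaged for each patient", and the averages are taken over four windows: "averaged for each patient across the 72-hour acute postoperative period, the following week, after 10 days, and overall". Each average goes to a one-sample t-test or signed-rank test. Section 5.6 gives no reference value for these tests. The only one appears in Section 5.6.1, where each test "only requires data from 13 patients to demonstrate a significant difference from zero", and 43 VR patients are said to be needed for a 10% reduction. Both figures assume 20% attrition, a 5% Type I error rate and 80% power. The only final criterion is the general one, "with p-values of <0.05 considered statistically significant".

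The second primary endpoint is a reduction of at least 20% in consumption over 90 days. It is tested by comparing mean daily MME between groups, and sized on 12.5 mg per day with SD 3.

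**The concern.** The endpoint names a size of effect, while the test asks only whether there is any effect. The plan never joins the two. A significant result could be reported as meeting the 20% endpoint when the mean drop is far smaller. Because no window is decisive, the window that counts could also be chosen after the data are seen. The same gap affects the opioid primary, which carries the opioid-sparing claim. Section 8 says that the data will go into a de novo submission to the FDA, so it matters exactly what a positive result is allowed to mean.

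A related gap is that 13 and 43 come without the SD or the scale that produced them. The reader cannot tell whether they size the relative endpoint that Section 5.6 defines.

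**Working it through.** **1. Reproducing 13 and 43.** One-sample t-test against zero, two-sided 5%, 80% power, exact (noncentral t), divided by 0.8 for attrition and rounded up.

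- Standardized effect d = 1.0: n = 10; 10/0.8 = 12.5, so 13.
- d = 0.5: n = 34; 34/0.8 = 42.5, so 43.

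Both match. One-sided tests would give 10 and 34 after attrition, so two-sided is the likely choice, though the plan does not say so. Two sets of inputs give these effects:

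- 2 points and 1 point over the stated SD of 2.0 (2/2.0 and 1/2.0). These equal 20% and 10% only at a pre-use score of 10; the highest mean in the plan is 8.50.
- 20% and 10% over a percent-change SD of 20 points (20/20 and 10/20). The plan states no such SD.

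**2. If SD 2.0 points applies to the change.** This is an assumption, because in Section 5.6.1 the figure describes standard-of-care pain scores. The means 8.50 and 6.16 are from the same section.

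| True drop | Points | d | n | Enrolled | Power, 40 completers |
|---|---|---|---|---|---|
| 20% of 8.50 | 1.70 | 0.85 | 13 | 17 | 99.9% |
| 20% of 6.16 | 1.232 | 0.616 | 23 | 29 | 97% |
| 10% of 8.50 | 0.85 | 0.425 | 46 | 58 | 75% |
| 10% of 6.16 | 0.616 | 0.308 | 85 | 107 | 48% |

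Forty completers is the planned 50 VR patients less 20%.

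**3. Smallest mean drop that is significant against zero.** This is SD × t(0.975, 39)/√40 = SD × 2.023/6.325 = SD × 0.320. The SD of percent change is assumed; 32.5 is 2.0/6.16.

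| Assumed SD (percentage points) | 15 | 20 | 32.5 | 40 |
|---|---|---|---|---|
| Smallest significant drop | 4.8% | 6.4% | 10.4% | 12.8% |
| Chance of p<0.05 if true drop is 10% | 98% | 87% | 48% | 34% |

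**4. Four windows.** Simulation with no effect, 40 patients and 40,000 trials. The three separate windows were given 9, 21 and 12 uses (three a day for 3, 7 and 4 days), and the overall window is their weighted mean. The chance that at least one of the four tests gives p<0.05 is 16%, 14%, 13% and 10% for an assumed between-window correlation of 0, 0.3, 0.5 and 0.8.

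**5. Opioid primary.** The smallest significant difference is t × 3 × √(2/n).

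- n = 37 per group (50 less the stated 25%): 1.993 × 3 × √(2/37) = 1.39 mg; 1.39/12.5 = 11.1%.
- n = 50 per group: 1.984 × 3 × √(2/50) = 1.19 mg; 1.19/12.5 = 9.5%.

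Both fall well short of 20% (2.5 mg). With 37 per group, only observed differences of 20% or more would be significant once the SD reaches about 3 × 20/11.12 = 5.4.

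**The case against.** Sizing and testing against zero is ordinary practice and not an error in itself. Section 5.6 does hold a 20% benchmark: its example asks for a mean of 6.4 from a starting score of 8. That stands, so it would be too strong to say that the plan has no 20% standard. What is missing is how the benchmark combines with the test. Section 5.6 also gives a reason for looking at every stage of recovery. That justifies having several windows, but it does not say which one decides.

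A reader might infer from step 2 that 13 and 43 are wrong, or that the trial is too small. The documents do not support either. Section 5.6.1 words both effects as percentages, and a percent-change SD of 20 points makes both numbers exactly right. The SD of 2.0 points comes from a different quantity, so the SD of a patient's averaged within-use change may be smaller or larger. Power for the 20% effect against zero stays adequate even at SD 2.0 points (97% at 6.16). Any shortfall concerns only the 10% figure, which the plan offers as an example.

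A reader might also infer that averaging percent change over uses undermines the endpoint, since it is undefined when pain starts at 0. In simulations with a true 20% drop and an assumed rating error of SD 1, at mean pain of 4.93 to 8.50, at most 2.3% of uses were undefined and the average lay between −15% and −20%. That bias is modest and runs toward a smaller effect. The plan also calls the repeated uses data "requiring linear mixed model analysis to assess acute changes in pain scores". A rule for zero scores is needed; a new primary score is not.

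**Conclusion.** The concern holds for the decision rule and the deciding window, and both should be settled before the data are seen. At every SD considered (15 to 40 percentage points, assumed), significance with 40 completers can come from an observed mean drop well under 20%, so p<0.05 does not show that the acute endpoint was met. Leaving the window open roughly doubles to triples the 5% false-positive rate if any one window may count, given the assumed correlations. The opioid result rests on the plan's own SD of 3 and would weaken if variability proves much larger.

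For the sample sizes the conclusion is narrower. The basis of 13 and 43 is not stated, and one of the two readings that reproduce them does not fit the relative definition. If SD 2.0 points is what was used, a 10% drop needs 58 to 107 enrolled, against 43 stated and 50 planned.

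**What to change.** 1. **Window.** Name one window in advance as the single primary acute test and make the other three supportive. The overall 14 days is a natural choice, but any one will do if fixed beforehand.
2. **Decision wording.** Keep the test against zero and describe it only as showing a reduction greater than zero. Report the estimate and 95% CI against 20%. Say that the 20% benchmark was reached in the sample only if the test is significant and the estimate is at least 20%. Say that a reduction of at least 20% was demonstrated only if the CI excludes smaller reductions. Do not label the estimate rule as being consistent with 20%: at SD 20, an estimate of 18% has a CI of 18 ± 6.4, or 11.6% to 24.4%, which includes 20% yet fails the rule. Use the same wording for the opioid primary.
3. **Sizing.** State the SD, its scale and the sidedness behind 13 and 43. Restate both numbers if the SD is 2.0 points. Reconcile the alternative of 20% or 2 points in Aim 1 with the relative definition in Section 5.6.
4. **Minor.** State how uses with a pre-use score of 0 are handled. Report a ratio of mean post-use to mean pre-use pain, or the absolute change in the planned mixed model, as a sensitivity analysis without replacing the primary score.

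The cost is plan wording and a restated calculation, with no new data. There are downsides. When the true drop is exactly 20%, the estimate rule is met only about half the time. A demonstrated 20% needs a true drop of about 29% for 80% probability at SD 20 with 40 completers. The restated sizes may look less favourable. In return, a true drop of only 10% would meet the estimate rule in about 0.1% of trials at SD 20 and 5.7% at SD 40, against 87% and 34% for p<0.05 alone.
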